---

## Acronyms

CrI	credible interval
DBS	dried blood spot
HRP2	histidine-rich protein 2
HRP3	histidine-rich protein 3
LDH	lactate dehydrogenase
PCR	polymerase chain reaction
PDS	panel detection score
pfhrp2	Plasmodium falciparum histidine-rich protein 2
pfhrp3	Plasmodium falciparum histidine-rich protein 3
RDT	rapid diagnostic test
WHO	World Health Organization

## Disclaimers

1. This recommended master protocol has been developed by the World Health Organization (WHO) to guide surveillance and biobanking for *pfhrp2/3* gene deletions in malaria-endemic countries; however, WHO cannot accept any responsibility or liability for the conduct of studies by third parties that follow the protocol.
2. Studies conducted by third parties pursuant to the protocol cannot be considered “WHO studies”. Appropriate approval(s) at local and/or national level should be obtained prior to the start of any such study.

# 1. Project summary

Title	
Study site(s)	Site 1: Name, city, district and province Site 2: Name, city, district and province Site 3: Name, city, district and province (Add more sites as needed, or include just counties and add an annex with a list of health facilities)
Protocol submission date	dd/mm/yyyy
Protocol number	Unique protocol number/version number
Principal investigator	Name: Degree: Institution: Address: street, city, postal code, country Tel: Email:
Co-investigators (insert additional name(s) if needed)	Name: Degree: Institution: Address: street, city, postal code, country Tel: Email:
Participating institutions (insert additional institution(s) if needed)	Name: Complete postal address: street, city, postal code, country Tel: Email:
Planned study dates	From mm/yyyy to mm/yyyy
Sponsor	Ministry of Health, country Complete postal address: street, city, postal code, country Tel: Email:

Objectives	
This survey is intended to determine whether the local prevalence of false-negative rapid diagnostic test (RDT) results caused by Plasmodium falciparum histidine-rich protein 2/3 (pfhrp2/3) gene deletions has reached a threshold that would require a local or national change in diagnostic strategy. The specific objectives are to:
 
 
1. measure the prevalence of false-negative HRP2 RDT results caused by pfhrp2/3 gene deletions among all symptomatic P. falciparum confirmed cases
 
2. measure the prevalence of suspected false-negative HRP2 RDT results among symptomatic patients attending public health facilities with P. falciparum infection detected by microscopy or a P. falciparum lactate dehydrogenase (Pf-LDH) RDT;
 
3. identify domains (e.g. provinces, states or districts) in which the prevalence of false-negative HRP2 RDTs results caused by pfhrp2/3 gene deletions is above 5%, warranting a change of RDTs.
 
4. determine the predictive value of false-negative HRP2 RDT results for pfhrp2/3 gene deletions in different settings; and
 
5. The biobanking activity is intended to support future malaria epidemiological research and the development of new and/or improved health products, particularly those targeting pfhrp2/3-deleted parasites.
 

Surveillance site	Pre-selected public health facilities representing the spectrum of transmission and geographical diversity across the country
Target population	Individuals meeting the case definition for suspected malaria case
Survey type	Cross-sectional, multi-site
Primary output measures	
 
1. Prevalence of false-negative HRP2 RDT results caused by pfhrp2/3 gene deletions among all symptomatic P. falciparum confirmed cases
 
2. Prevalence of suspected false-negative HRP2 RDT results among symptomatic patients with P. falciparum malaria
 
3. Prevalence of pfhrp2/3 gene deletions among symptomatic P. falciparum patients with a false-negative HRP2 RDT result
 

Secondary output measures (optional)	
 
1. Parasite density, as measured by quantitative PCR and/or microscopy, in patients with suspected false-negative HRP2 RDT results
 
2. Improved understanding of pfhrp2/3 gene deletions, e.g. genetic relatedness and/or drug resistance and fitness, and new and/or improved diagnostic tools for detecting pfhrp2/3-deleted parasites
 
3. Prevalence of parasites with pfhrp2/3 deletions among all symptomatic P. falciparum confirmed cases
 
4. Estimates of the intra-cluster correlation in the prevalence of pfhrp2/3 deletions within sampling domains (e.g. provinces or districts), or other measures of heterogeneity that can help guide future studies
 

Sample size	
A sample size of 300 confirmed P. falciparum cases per sampling domain (30 cases in each of 10 health facilities) is a default proposition to quantify whether or not the prevalence of false-negative RDT results caused by pfhrp2 deletions is above 5%. A sampling domain can be a province, district, state or something else, depending on the administrative boundaries of the country. Once the sample of 300 P. falciparum cases has been enrolled, then molecular confirmation of pfhrp2/3 deletions among suspected false-negative P. falciparum cases should ensue. While 300 confirmed P. falciparum cases is the default sample size, a sample size table is provided to allow for some flexibility. A tool has also been created for customized sample size estimates informed by baseline knowledge and desired power.

## Sampling method

A cross-sectional survey will measure the suspected and confirmed prevalence of false-negative HRP2 RDT results caused by *pfhrp2/3* gene deletions in multiple pre-selected health facilities per sampling domain, e.g. provinces at risk.

## Data collection

1. Identify domains (e.g. provinces, districts) to be included in the study. Factors to consider include: (i) capturing a range of transmission strata, (ii) ensuring broad geographical representation, and (iii) optionally, weighting based on population at risk.
2. Select 10 health facilities per domain for testing (if this is not possible, a smaller number of health facilities may be viable; see Table 2 for variations in the number of health facilities and recommended sample numbers). Any facility in which RDTs are being used is eligible; microscopy services are not a requirement. Selection of health facilities may be through randomization or deliberate choice (e.g. sentinel surveillance), and must ensure balanced representation of the target population.
3. In the target population (suspected malaria cases), conduct routine case management procedures and obtain informed consent (or assent, depending on the age of majority and federal guidelines in the country of enrolment) to perform an additional RDT and collect at least two dried blood spots (DBSs) for laboratory analysis and for biobanking/long-term storage to support future malaria epidemiological and diagnostic research.
4. Take clinical history, including questions regarding age, sex, recent malaria diagnostic testing, antimalarial therapy and travel.
5. Test all consenting suspected malaria cases simultaneously using both a WHO-recommended HRP2 RDT and a non-HRP2-based method (e.g. Pf-LDH RDT (separate single or multiple test line RDT)) or quality-assured microscopy in the health facility, and collect a minimum of two DBSs on filter paper or protein saver cards.
6. Record demographic and clinical history details and all test results on the survey report form.
7. Administer antimalarial therapy based on results from (either) RDT and/or microscopy, according to national guidelines.
8. Retain used RDTs for quality control and a minimum of two DBSs from all consenting *P. falciparum* patients for molecular +/- serological analysis.
9. Enrolment can stop once 30 individuals with confirmed *P. falciparum* malaria from each of 10 health facilities have been recorded in the survey tally sheet as having *P. falciparum* (a different number of confirmed individuals is required per health facility if using other than 10 clusters; see Table 2).
10. Ship all consent forms, tally sheets, survey report forms and patient samples to the central coordinating centre.
11. Central laboratory staff review survey report forms, identify the suspected *pfhrp2/3* deletion cases and prioritize these DBSs for molecular +/- serological analysis.
12. Proceed with supplemental data analysis according to prioritization and resources available, i.e. HRP2-positive samples, and HRP2- and Pf-LDH-negative samples; options are described in Annex 1.
13. Discard all RDTs, microscopy slides and DBSs after survey results have been finalized and reported, unless consent for long-term storage of DBSs has been obtained.

## 2. Background and rationale

Rapid diagnostic test (RDT) kits offer great potential for the immediate diagnosis of malaria infections. Rapid diagnosis allows for prompt treatment, especially in rural settings. RDTs are lateral flow immunochromatographic tests that detect *Plasmodium* parasite antigens in blood (1). Three antigens are detected by current RDTs: histidine-rich protein 2 (HRP2), lactate dehydrogenase (LDH) and aldolase. HRP2 is an abundant protein expressed only by *P. falciparum* and is the target of the most commonly used RDTs. Although the antibodies on the test strip are designed to recognize the HRP2 antigen, they may also cross-react with another antigen of the HRP family, namely HRP3, due to strong similarities in the amino acid sequences (2). HRP2-based RDTs tend to be more sensitive and heat-stable than RDTs that detect LDH or aldolase (3).

While HRP2-based RDTs generally have the highest sensitivity of the RDTs for detecting *P. falciparum* malaria (3), parasite strains have recently been identified that have deletions in the genes encoding the HRP2 or similar HRP3 protein. Strains with both *pfhrp2* and *pfhrp3* gene deletions are undetectable by HRP2-based RDTs (4). HRP2-based RDTs can sometimes still detect strains with only a *pfhrp2* deletion, particularly in high parasite density infections, due to antibody cross-reactivity with epitopes of HRP3 (4). In 2010, Gamboa *et al.* (5) first reported the identification of *P. falciparum* parasites with *pfhrp2/3* gene deletions in the Amazon River basin in Peru. Subsequent retrospective analyses at different sites in the Loreto region of the Peruvian Amazon showed an increase in the prevalence of parasites with gene deletions from specimens collected in 1998–2001 (20.7%) to those collected in 2003–2005 (40.6%) (6). The prevalence of parasites with *pfhrp2/3* gene deletions shows substantial local variability. Studies in other countries, such as Colombia (7,8), Ghana (9), Guyana (10), Honduras (11), India (12), Mali (13), Myanmar (14), Senegal (15) and Suriname (10), have found very different prevalence estimates, although the rigour of study design has been variable. In Africa, published data from Eritrea showed the prevalence of dual *pfhrp2* and *pfhrp3* deletions to be very high (80%), requiring an urgent response and policy change away from a testing strategy relying solely on HRP2 (16). There have been no reports of parasites failing to express LDH or aldolase, as these targets are essential enzymes for parasite metabolism and survival. Subsequently, other countries in the Horn of Africa, such as Djibouti (17) and Ethiopia (18–20), also reported a high prevalence of *pfhrp2* and *pfhrp3* deletions, which led to the adoption of non-HRP2-based RDTs for diagnosis.

In settings where microscopy is either unavailable or infeasible due to time or resource constraints, it is imperative that malaria be treated based on RDT results. Monitoring the accuracy of the RDT results is thus critical. The main causes of false-negative RDT results are related to product quality and performance, transportation or storage conditions, operator error, or parasite density below the limit of detection; however, deletions of the genes encoding the target antigen must also be considered (4). To avert a crisis like the one that emerged in Eritrea in 2016, WHO recommends that countries where *pfhrp2/3* deletions have been reported, as well as neighbouring countries, conduct surveillance for *pfhrp2/3* deletions, particularly among symptomatic patients (3).

The purpose of WHO-recommended surveillance for *pfhrp2/3* deletions is to identify areas where the prevalence of false-negative RDT results caused by *pfhrp2/3* gene deletions is more than 5%, as this is the recommended threshold for switching to non-HRP2-based RDTs. In this context, it is important to point out that the prevalence of *pfhrp2* deletions in a population may be much higher than 5% to cause > 5% false-negative RDT results, as a number of biological factors can influence this outcome. These factors include expression of the *pfhrp3* gene in *pfhrp2*-deleted parasites (with the HRP3 antigen causing positive RDT results due to its cross-reactivity with HRP2 RDTs) and the prevalence of polyclonal infections (with *pfhrp2*-deleted and non-deleted parasites

coexisting in the same host) in a population (21). The prevalence of deletions may also need to be higher than 5% in order to confidently conclude that the threshold has been exceeded, based on the statistical analysis.

The purpose of this document is to present a standardized protocol that *P. falciparum*-endemic countries can use to identify the prevalence of false-negative HRP2 RDT results caused by *pfhrp2/3* gene deletions among symptomatic falciparum patients. The methods contained herein can be used to map the distribution of these deletions, estimate the predictive value of suspected false-negative HRP2 RDT results for gene deletions, and identify areas where diagnostic strategies may need to be changed.

### 3. Survey and research objectives

This survey is primarily intended to determine whether the local prevalence of false-negative HRP2 RDT results caused by *pfhrp2/3* gene deletions among symptomatic falciparum patients has reached a threshold that should trigger a national or subnational change of malaria RDTs. The specific objectives are as follows:

1. Measure the prevalence of false-negative HRP2 RDT results caused by *pfhrp2/3* gene deletions among all symptomatic *P. falciparum* confirmed cases
2. Measure the prevalence of suspected *pfhrp2/3* gene deletions among symptomatic falciparum patients attending public health facilities.
3. Identify domains that have greater than 5% false-negative RDT results caused by *pfhrp2/3* gene deletions in these patients, as this indicates a need to switch from using exclusively HRP2-based RDTs for detecting *P. falciparum*.
4. Determine the predictive value of suspected false-negative HRP2 RDT results for *pfhrp2/3* gene deletions in different settings.
5. Support future malaria epidemiological research and product research and development for malaria.

### 4. Survey site(s)/target population

This surveillance activity will focus on suspected malaria cases seeking care at public health facilities. Test results that are negative for *P. falciparum* by HRP2 RDT but positive by Pf-LDH RDT or microscopy indicate that *pfhrp2/3* gene deletions may be the reason for the false-negative HRP2 result. Given the importance of HRP2 detection to the diagnostic strategy, the World Health Organization (WHO) is urging at-risk countries to assess the prevalence of such false-negative HRP2 RDT results caused by *P. falciparum* gene deletions. Prioritized for surveillance are areas (i) with a recognized discordance between HRP2 RDT and microscopy results, (ii) with non-representative or sporadic reports of *pfhrp2/3* deletions in the country, and (iii) that are neighbouring an area where frequent *pfhrp2/3* deletions have been identified. In such countries, public health facilities in all areas of *P. falciparum* malaria transmission should be included. Facilities eligible for inclusion in the study should ideally represent the geographical spread of malaria transmission across the sampling domain.

## 4.1 Inclusion criteria

- Participants should meet the case definition for suspected malaria case

## 4.2 Exclusion criteria

- Participants should be excluded if they have been previously enrolled in the survey

# 5. Survey methods

## 5.1 Design

A cross-sectional survey design will be used to measure the primary outputs. Health facilities will systematically test suspected malaria cases with an HRP2-based RDT and an alternative method (i.e. Pf-LDH RDT or microscopy) and collect a minimum of two dried blood spots (DBSs). Although this approach is the direct and preferable method for this type of survey, an alternative approach using high-throughput immunoassays may be considered when RDT screening data are not available. In addition, immunoassays are useful for confirming the presence or absence of HRP2/3 proteins, especially when RDT and polymerase chain reaction (PCR) results for HRP2 status do not match. The details of this approach are provided in Annex 2.

The prevalence of suspected false-negative HRP2 RDT results among symptomatic patients with *P. falciparum* malaria is a primary output (output 2). Molecular testing of the DBSs from cases with suspected false-negative HRP2 RDT results will determine the prevalence of false-negative HRP2 RDT results caused by *pfhrp2/3* gene deletions all symptomatic *P. falciparum* confirmed cases enrolled in the survey (output 1) and among false-negative HRP2 RDT patients (output 3).

## 5.2 Primary output indicators

The following indicators will serve as the primary survey outputs:

1. prevalence of false-negative HRP2 RDT results caused by *pfhrp2/3* gene deletions among all symptomatic *P. falciparum* confirmed cases;
2. prevalence of suspected false-negative HRP2 RDT results (i.e. a negative HRP2 RDT result but a positive result by Pf-LDH RDT or *P. falciparum* microscopy, or HRP2-negative but Pf-LDH-positive in a serological test) among symptomatic patients with *P. falciparum* malaria; and
3. prevalence of *pfhrp2/3* gene deletions among symptomatic falciparum patients with a false-negative HRP2 RDT result.

The survey will identify the proportion of patients with suspected false-negative HRP2 RDT results through diagnostic testing at health facilities, using dual-method testing (HRP2 RDT plus microscopy or Pf-LDH RDT). To save time and resources, molecular +/- serological testing to confirm *P. falciparum* infection and identify *pfhrp2/3* deletions will prioritize DBSs collected from individuals with suspected false-negative HRP2 RDT results. Discordant diagnostic results may be due to other factors, such as false-positive Pf-LDH test lines (possibly due to cross-reactivity with non-falciparum species) or low parasite densities at

---

1 RDTs should be used that contain Pf-LDH-specific test lines and not pan-pLDH test lines. This will ensure that only *P. falciparum* infections are detected and avoid the identification of non-falciparum species (*P. vivax*, *P. malariae*, *P. ovale*), which would cause discordant results (HRP2-negative, pan-pLDH-positive).

or below the limit of detection of the HRP2 and Pf-LDH RDTs. In addition, there are several situations in which this indicator could miss a true *pfhrp2/3* gene deletion (see Table 1). First, individuals will not be detected if they have a low-density infection that is missed by Pf-LDH RDT or microscopy and also missed by HRP2 RDT because of *pfhrp2/3* gene deletion. Second, HRP2 RDTs may still detect some infections with a *pfhrp2* deletion due to cross-reactivity of test antibodies with HRP3. Finally, the testing protocol will not detect *pfhrp2/3* deletions in patients coinfecting with HRP2-expressing clones, unless certain techniques are used, such as quantitative PCR (22–24), deep sequencing (25,26) and digital PCR (27). For these reasons, this indicator represents the lower limit of the true prevalence of *pfhrp2/3* gene deletions but should detect all clinically significant *pfhrp2/3* deletions.

**Table 1. Summary of test result combinations and limitations of the approach, including only individuals with discordant HRP2 RDT results (positive by Pf-LDH or microscopy AND negative by HRP2 RDT)**

HRP2 RDT	Pf-LDH RDT or microscopy	Molecular analysis performed a	Interpretation of results and limitations in detecting pfhrp2/3 deletions
+	+	No	
 
• May be infection with pfhrp2 deletions but HRP3 was detected by HRP2 RDT
 
• May be multiclonal infection with parasites with and without pfhrp2/3 deletions
 

+	-	No	
 
• False-positive HRP2 RDT (or persisting HRP2 after resolution of infection)
 
• May be infection with pfhrp2 deletions but HRP3 was detected by HRP2 RDT, or may be multiclonal infection with parasites with and without pfhrp2/3 deletions
 
 
and
 
 
• Low parasite density at or below the limit of detection of Pf-LDH RDTs and/or microscopy
 

-	+	Yes	
 
• False-positive Pf-LDH RDT or microscopy
 
• Low parasite density at limit of detection of RDTs (variable reactivity of test lines)
 

-	-	No	
 
• Cannot exclude low-density infection missed by both RDTs and microscopy, with undetected pfhrp2/3 deletions
 

a While all HRP2-negative and Pf-LDH/microscopy-positive samples should undergo molecular analysis, it is recommended that a subset of the other categories also be analysed.

### 5.3 Secondary output indicators (optional)

1. parasite density, as measured by quantitative PCR and/or microscopy, in patients with suspected false-negative HRP2 RDT results;
2. improved understanding of *pfhrp2/3* gene deletions, e.g. genetic relatedness and/or drug resistance and fitness, and new and/or improved diagnostic tools for detecting *pfhrp2/3*-deleted parasites;
3. prevalence of parasites with *pfhrp2/3* deletions among all symptomatic *P. falciparum* confirmed cases; and
4. estimates of the intra-cluster correlation in the prevalence of *pfhrp2/3* deletions within sampling domains (e.g. provinces or districts), or other measures of heterogeneity than can help guide future studies.

## 5.4 Statistical analysis plan and sample size

The aim of the statistical analysis is to identify survey domains (provinces, districts, states or similar) where there is a high probability that the prevalence of false-negative HRP2 RDT results caused by *pfhrp2* gene deletions is above 5%. Unlike previous versions of the protocol, here, the focus is on identifying areas that are above the threshold (one-tailed test), rather than above or below the threshold (two-tailed test).

Raw data consist of counts of the number of confirmed false-negative HRP2 RDT results caused by *pfhrp2* gene deletions (numerator) and the number of confirmed and enrolled *P. falciparum* cases (denominator) in each health facility. These can be fed into the software package DRpower, accessible via an interactive web app (<https://shiny.dide.ic.ac.uk/DRpower-app/>). This software uses a Bayesian hierarchical model to estimate the prevalence of false-negative HRP2 RDT results caused by *pfhrp2* gene deletions, while accounting for correlations within clusters (for more information on the model, see Annex 3). The software returns a point estimate of the prevalence along with a 95% credible interval (CrI). This information should be presented when summarizing results, but should not be used directly to decide whether a domain is above the threshold. That decision is based on another output of the software: the probability that the prevalence of false-negative HRP2 RDT results caused by *pfhrp2/3* deletions is above 5%. This value is used to categorize study domains as follows:

**Outcome 1:** The posterior probability of being above the 5% threshold is less than 0.95. In this case, there is not sufficient evidence to conclude that the proportion of false-negative HRP2 RDT results caused by *pfhrp2/3* deletions among symptomatic *P. falciparum* patients is greater than 5%.

**Outcome 2:** The posterior probability of being above the 5% threshold is greater than or equal to 0.95. In this case, there is high statistical confidence that the proportion of false-negative HRP2 RDT results caused by *pfhrp2/3* deletions among symptomatic *P. falciparum* patients is greater than 5%.

Programmatic decisions can be made on the basis of these outcomes. Note that it is possible for the CrI to span the 5% threshold when the probability of being above 5% is greater than 0.95 (because the CrI is two-tailed but the statistical test is one-tailed).

Sample sizes are chosen to ensure a high probability (80% or more) of finding outcome 2 when the true prevalence of false-negative HRP2 RDT results caused by *pfhrp2/3* gene deletions is above 5%. As the prevalence gets closer to the 5% threshold, it becomes increasingly difficult to prove that prevalence is above this threshold, leading to large sample sizes. Therefore, 10% is used as representative of a high-prevalence setting, striking a balance between sensitivity and the need for sample sizes that are logistically feasible to collect. Consequently, in areas where outcome 2 is found, the prevalence of false-negative HRP2 RDT results caused by *pfhrp2/3* gene deletions will typically be significantly higher than 5%.

Table 2 gives the sample size required to achieve 80% power using the analysis approach proposed above. This table gives the total number of confirmed *P. falciparum* positive cases required (minimum required) for inclusion in the study. A key point to highlight in this example is that the random selection of at least 10 sites per domain will require enrolment of 300 *P. falciparum* confirmed cases, while a reduction in the number of sites will increase the number of samples required to achieve statistical power (i.e. selection of only six sites will require 678 confirmed malaria cases).

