**Table 2. Sample size required to achieve 80% power using the proposed analysis**

Number of clusters (health facilities)	Sample size per cluster	Total sample size
1	--	--
2	--	--
3	--	--
4	--	--
5	496	2 480
6	113	678
7	68	476
8	51	408
9	37	333
10	30	300

Not all suspected malaria patients test positive for falciparum malaria. Therefore, to calculate the number of suspected *P. falciparum* cases to enroll, these numbers should be divided by the expected positivity rate. For example, if 40% of suspected *P. falciparum* cases are expected to come back positive, then the sample of 30 positive cases per cluster increases to 75 (30/0.4) suspected cases to enroll. This number should be further buffered to account for potential drop-out, e.g. due to sequencing failure or diagnostic accuracy. Finally, sample sizes may differ from one health facility to the next; the power of study designs with variable cluster sizes can be explored in the DRpower software and interactive web app (<https://shiny.dide.ic.ac.uk/DRpower-app/>).

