Next, priors are defined on  $p$  and  $r$ . For the prevalence of deletions,  $p$ , a uniform prior is assumed over the range  $[0, 1]$  so as to not preempt the possibility of it being any particular value. For the ICC,  $r$ , a  $\text{Beta}(1, 9)$  prior is assumed, which places more probability density on small values, typically in the range  $[0, 0.3]$ . This prior is based on an analysis of historical *pfhrp2/3* studies, in which the ICC was commonly estimated to be in this range. The marginal posterior distribution of the prevalence is obtained by multiplying the likelihood in (A3) by these priors and integrating out the ICC:

$$\Pr(p|\mathbf{k}, \mathbf{n}) \propto \int_0^1 \Pr(\mathbf{k}|\mathbf{n}, p, r) \Pr(p) \Pr(r) dr. \quad (\text{A4})$$

This integration is performed numerically in DRpower via a quadrature-based method. The posterior distribution in (A4) can be summarized in various ways, for example in terms of the maximum a posteriori (MAP) estimate and the 95% CrI. To establish whether prevalence is above a given threshold  $\mu$  (typically 5%), the posterior distribution over all values of  $p$  greater than  $\mu$  can be integrated:

$$\Pr(P > \mu|\mathbf{k}, \mathbf{n}) = \int_{\mu}^1 \Pr(p|\mathbf{k}, \mathbf{n}) dp. \quad (\text{A5})$$

If this probability is greater than a predesignated value (0.95 by default), we conclude that prevalence is above  $\mu$ ; otherwise, we conclude that prevalence is below  $\mu$ . This is a Bayesian hypothesis test, meaning that it directly compares two competing hypotheses rather than trying to disprove a single null hypothesis.

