### Power and sample size calculation

Unfortunately, there is no simple formula for statistical power under this model. Instead, a simulation is undertaken as follows:

1. Define the global prevalence of deletions ( $p$ ), the ICC ( $r$ ) and the number of clusters ( $c$ ).
2. Define the per-cluster sample size ( $n$ ) to be the same in all clusters ( $n_i = n$ ).
3. Simulate a data set of deletion counts ( $\mathbf{k}$ ) from the beta-binomial model described above using these values of  $p$ ,  $r$ ,  $c$ ,  $n$ .
4. Analyze this simulated data set using the Bayesian framework above. Determine if the correct conclusion is reached, i.e. that  $p > \mu$  if this is indeed the case.
5. Repeat steps 3–4 many times (typically 1000 or more) to establish the proportion of times the correct conclusion is reached. This is referred to as the **empirical power**.
6. Repeat steps 2–5 over a range of values of  $n$ . Construct an empirical power curve and find the value of  $n$  at which power crosses the target level, typically 80%. This is the minimum sample size  $n_{opt}$  for this parameter combination.
7. Repeat steps 1–6 for a range of parameter combinations to produce sample size tables.

Table 2 in the protocol was produced using this method, assuming a fixed value of  $r = 0.05$ . This value is based on an analysis of historical *pfhrp2/3* deletion studies, in which the mean estimate of the ICC is around this level. Note that the sample size tables produced using this method are only valid if the intention is to analyze data using the DRpower Bayesian model. If the plan is to use a different analysis approach, then a different power and sample size analysis is required.

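### Section 5.4 promises at least 80% power whenever true prevalence is above 5%, but Table 2 is built for a prevalence of 10% and an ICC of 0.05; at 6 to 9% the default design has about 20 to 69% power

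*Protocol*

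**What the plan says.** Section 5.4 of the protocol classifies each domain by one rule. Outcome 2 is declared when "The posterior probability of being above the 5% threshold is greater than or equal to 0.95"; otherwise the domain gets Outcome 1. The section describes the purpose as one-sided: "the focus is on identifying areas that are above the threshold (one-tailed test").

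The paragraph on sample size opens with the promise "Sample sizes are chosen to ensure a high probability (80% or more) of finding outcome 2 when the true prevalence" is above 5%. It then qualifies itself: "As the prevalence gets closer to the 5% threshold, it becomes increasingly difficult to prove that prevalence is above this threshold". It goes on: "Therefore, 10% is used as representative of a high-prevalence setting", as a compromise with what can feasibly be enrolled.

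Table 2 follows under the title "Sample size required to achieve 80% power using the proposed analysis". The title names neither a prevalence nor an ICC. The ICC is given only in Annex 3 (Power and sample size calculation): Table 2 uses a fixed value of 0.05, taken from historical studies "in which the mean estimate of the ICC is around this level". Annex 3 also sets the analysis prior for the ICC: a Beta(1, 9) "prior is assumed, which places more probability density on small values", typically between 0 and 0.3, and likewise attributed to historical studies.

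The protocol gives no power figure for any prevalence between 5% and 10%, or for any other ICC.

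**The concern.** A prevalence above 5% includes 6, 7, 8 and 9%. Power calculated at 10% cannot carry over to those values, and the protocol itself says that proof gets harder near the threshold. The opening sentence therefore claims a property that the design was not built to have.

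This bears on how Outcome 1 is read. Under section 5.6, Outcome 2 in any domain leads to a nationwide change of test, while Outcome 1 in all domains leads to a repeat survey in two years or sooner. Annex 3 also says that when the 0.95 criterion is not met, prevalence is concluded to be below the threshold, which is stronger than the insufficient-evidence wording of section 5.4. Beside a promise of 80% detection for anything above 5%, this invites a programme to take Outcome 1 as reassurance.

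The document is a master protocol for countries to adapt, so the sentence and the table may well be copied without Annex 3. Section 5.5 already treats unequal facility sizes as valid if overall power is still 80%, without saying at what prevalence or ICC.

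**Working it through.** **Inputs, all from the protocol**
- Default design: 10 facilities × 30 confirmed cases = 300 (section 5.4, Table 2).
- Design prevalence 10% (section 5.4); planning ICC r = 0.05 (Annex 3).
- Priors: prevalence p uniform on 0 to 1; r ~ Beta(1, 9) (Annex 3).
- Rule: Outcome 2 if Pr(p > 0.05 | data) ≥ 0.95 (section 5.4).

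**Method.** Annex 3 gives no closed formula, so its simulation steps were followed.
1. Draw each facility's prevalence from Beta(p(1/r − 1), (1 − p)(1/r − 1)). At p = 0.10 and r = 0.05, 1/r − 1 = 19, so this is Beta(1.9, 17.1).
2. Draw each facility's count from a binomial with n = 30.
3. Compute the posterior of p on a grid, integrating out r under its prior.
4. Apply the rule. Power is the share of simulated surveys with Outcome 2.

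The cells for the default design used 10,000 to 20,000 surveys each (Monte Carlo standard error about 0.3 to 0.5 points).

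**The protocol's own figure.** At p = 10% and r = 0.05, repeat runs for 10 × 30 gave 81.1 to 82.6%. The other rows of Table 2, at 4,000 surveys each, gave:

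| Facilities × cases | Power |
|---|---|
| 5 × 496 | 79.0% |
| 6 × 113 | 78.4% |
| 7 × 68 | 80.3% |
| 8 × 51 | 80.8% |
| 9 × 37 | 80.0% |

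All lie within about two points of 80%. Annex 3 mentions 1,000 or more surveys per point, for which the standard error is √(0.8 × 0.2 / 1,000) ≈ 1.3 points. Table 2 is sound on its inputs.

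**Varying the true prevalence (10 × 30, ICC 0.05)**

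| True prevalence | P(Outcome 2) | P(Outcome 1) |
|---|---|---|
| 6% | about 20% | about 80% |
| 7% | about 35% | about 65% |
| 8% | about 53% | about 47% |
| 9% | about 69% | about 31% |
| 10% | about 82% | about 18% |
| 11% | about 90% | about 10% |
| 12% | about 95% | about 5% |

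Other runs differ from these by up to about two points.

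**Varying the ICC (10 × 30, true prevalence 10%)**

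| ICC | P(Outcome 2) |
|---|---|
| 0.01 | 93% |
| 0.03 | 87% |
| 0.05 | 82% |
| 0.07 | 76% |
| 0.10 | 68–69% |
| 0.15 | 58% |
| 0.20 | 49% |

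The ICC of 0.10 is the mean of the analysis prior, 1/(1 + 9). Averaged over that whole prior, power at 10% prevalence is about 72%.

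**Would more cases per facility rescue the sentence?** With 10 facilities at ICC 0.05 and 1,500 surveys per cell, 60, 120 and 240 cases per facility gave 39%, 45% and 46% at a prevalence of 7%, and 61%, 65% and 70% at 8%. Even 10 × 240 = 2,400 cases falls short of 80%. The sentence has to change, since enlarging the facilities' samples does not make it true.

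**The case against.** The strongest defence is that the paragraph corrects itself. The next two sentences say that proof is harder near 5% and name 10% as the design value. The paragraph ends by saying that domains with Outcome 2 will typically lie well above 5%, and section 2 gives a similar warning. Annex 3 states the ICC for Table 2 by name. Section 5.4 defines Outcome 1 as insufficient evidence, and the protocol points users to software for other scenarios. This stands as far as disclosure goes: both assumptions can be found. It does not make the opening sentence true. The qualification carries no number and never withdraws the 5% claim, and a reader of the table alone sees neither assumption.

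Several stronger readings are tempting, and the documents do not support them.
- *Table 2 is miscalculated.* It reproduces on its stated inputs.
- *80% is reached only at exactly 10% and 0.05.* Power is about 90 to 95% at 11 to 12%, and at 10% prevalence it is 87% or more at an ICC of 0.03 or below.
- *Domains anywhere from 6 to 9% will mostly get Outcome 1.* That holds at 6 to 7%. At 8% it is about even, and at 9% Outcome 2 is likelier.
- *The ICC values contradict each other.* A historical mean near 0.05 can coexist with a diffuse prior. Beta(1, 9) has its mode at 0, a median of 1 − 0.5^(1/9) ≈ 0.074, and 1 − 0.95^9 ≈ 37% of its mass below 0.05. The Table 2 simulation already analyses its data under this prior. The mean of 0.10 is derived here; the protocol does not state it.

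**Conclusion.** The stated power property is wrong as written. For the default design, the 80% promise holds at a true prevalence of 10% or more with an ICC of 0.05 or less; it does not hold across the range above 5%. At ICC 0.05 the shortfall is large just above the threshold (about 20% power at 6% and 35% at 7%) and moderate at 8 to 9% (about 53% and 69%).

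The figures of 68% at ICC 0.10 and 49% at ICC 0.20 are sensitivity results. They show how far the 80% depends on the planning ICC, within a range that the protocol itself regards as typical. They do not refute the 80% at 0.05.

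This is a misstated property in the section that governs the decision. A reader might infer a faulty sample size or a hidden assumption, but the documents show neither. The figures rest on the Annex 3 model, equal facility sizes and the 0.95 rule. How programmes would in fact read Outcome 1 is a judgement that the documents cannot settle.

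**What to change.** 1. In section 5.4, end the opening sentence with: *when the true prevalence is 10% or more, assuming an ICC of 0.05*.
2. Put both assumptions in the Table 2 title.
3. For the default 10 × 30 design, report power at 6, 7, 8 and 9% prevalence (ICC 0.05), and at ICC 0.10 and 0.20 (10% prevalence).
4. State in section 5.4 that Outcome 1 is the likelier result for domains truly at 6 to 7%, and about even at 8%.
5. Add a line in Annex 3 explaining why the planning ICC is 0.05 while the prior, also drawn from historical studies, has mean 0.10.

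The cost is a few sentences and a short table that the existing software can produce. Sample sizes, the decision rule and Table 2's entries stay as they are. The stated power becomes less favourable, but it will be correct.
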